9.1.2.2 Adverse events during the fingolimod treatment period

Unless otherwise specified, all non-serious adverse events with onset on or after first dose date of fingolimod among all studies to last dose date of fingolimod + 45 days are included. All serious adverse events (SAEs) with onset on or after the first dose date of fingolimod among all studies are also included in the summaries. Also, unless otherwise specified, adverse events will be summarized for the fingolimod safety set, by primary system organ class and preferred term, and will show the number of patients with at least one adverse event and the incidence rate of adverse events per 100 patient-years in each SOC or PT category.

The AE incidence rate (IR) is calculated per 100 patient-years. IR is defined as: the number of patients experiencing at least one event in a particular category, over the total patient-years of the “at risk” population for that event multiplied by 100. An underlying Poisson process for incidence rate within treatment group is assumed.

To calculate the total patient-years (time at risk) of the “at risk” population:

1. For patients who have a particular AE category, sum the number of days from first dose date of fingolimod among all studies to the first occurrence of that particular AE category

2. For patients who did not have a particular AE category, sum the number of days from first dose date of fingolimod among all studies to last dose date of fingolimod + 45 days.
3. Add the time at risk for patients who had a particular AE category with the time at risk for patients who did NOT have a particular AE category. This is the total time at risk of that AE category.
4. Divide the total time at risk by 365.25.

Incidence rate of adverse events will be presented for the fingolimod safety set and for the subgroup of fingolimod safety set patients from phase II/III studies, by SOC and PT. Incidence rate of AEs, excluding AE listed in the core data sheet, will be presented by PT. Incidence rate of AEs that fulfill the risk search term (defined in the case retrieval sheet) will be presented by risk name and lower level terms. Similarly, all above indicated AE IR summaries will be conducted for SAEs.

To further evaluate the long-term AE rate (based on patient count and percentage) within a particular fingolimod treatment duration, an analysis based on yearly intervals since first dose of fingolimod will be conducted. For summaries on this set of patients, all AEs and SAEs with onset on or after first dose date of fingolimod (among all studies) to last dose date of fingolimod are included. Each yearly interval will contain 360 days. For example: Year 1 will consist of Day 1 to Day 360, Year 2 will consist of Day 361 to Day 720, Year 3 will consist of Day 721 to Day 1080, Year 4 will consist of Day 1081 to Day 1440, Year 5 will consist of Day 1441 to Day 1800, and so on. Patients will be summarized within a particular yearly interval if they have been receiving study treatment for at least one day in that particular interval. The number and percentage of these patients who have adverse events with onset date occurring during the interval will be summarized. For example, for the Year 1 group, patients with at least one day exposure to fingolimod will be included, and AEs with onset date occurring between Day 1 and Day 360 will be summarized. For the Year 2 group, patients with at least 361 days exposure to fingolimod will be included, and AEs with onset date occurring between Day 361 and Day 720 will be summarized. The same will be done for other intervals.

Adverse events summarized by year will include the following:

- Adverse events, by yearly interval, primary system organ class, and preferred term
- Serious adverse events, by yearly interval, primary system organ class, and preferred term
- Adverse events that fulfill the risk search term, by yearly interval
- Serious adverse events that fulfill the risk search term, by yearly interval

Intervals will be included based on the length of fingolimod exposure. Risk search terms are defined in Novartis' case retrieval sheet. Associated summaries will be presented by risk name and lower level terms.

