## 3 Investigational plan

### 3.1 Study design

This study uses an open-label, multi-center, single treatment arm design allowing patients participating in the fingolimod multiple sclerosis clinical development program to enroll in order to collect additional long-term safety, tolerability, efficacy, and health outcomes data.

This study has two parts:

[figure not shown]
- Part One, collecting long-term safety, tolerability, efficacy, and health outcomes data through approximately 30-Jun-2016, and
- Part Two\*, collecting limited safety data until approximately 30-Jun-2018, in a subset of patients participating in Part One, and other eligible patients from ongoing fingolimod trials (e.g., CFTY720D2312).

\*Eligibility for Part Two is defined as prior fingolimod study patients who are unable to obtain fingolimod outside a clinical trial.

By June 2016, investigators must determine commercial Gilenya eligibility for all active study patients (i.e., reimbursed for commercial Gilenya). Patients able to obtain commercial Gilenya will then have their End of Study (Part One) visit and exit the study, regardless of their post-study treatment decision (i.e., continuing on Gilenya commercially or transitioning to another treatment option). Patients discontinuing or completing the study at Part One who do not continue on commercial Gilenya must return for two follow-up study visits, 3-months and 6-months post-last dose of fingolimod. Patients who choose to continue on commercial Gilenya outside the study are exempted from the follow-up visits.

Patients not eligible for reimbursed, commercial Gilenya will be offered continued study participation in Part Two until their scheduled study visit closest to 30-Jun-2018 (+/- 30 day visit window), with a reduced assessment schedule (see Table 6-2), for the purpose of collecting additional long-term safety and tolerability data in support of the primary study objective. Patients discontinuing or completing the study after entering Part Two who do not continue on commercial Gilenya must return for one follow-up study visit, 3-months post-last dose of fingolimod. Patients who choose to continue on commercial Gilenya outside the study are exempted from the follow-up visit.

Patients enrolling in either part of the study from blinded studies will remain blinded to the identity of the treatment in the previous study. In order to maintain the blind, the monitoring

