### **5.5.9 Discontinuation of study treatment and premature patient withdrawal**

Patients may voluntarily withdraw from the study for any reason at any time. They may be considered withdrawn if they state an intention to withdraw, fail to return for visits, or become lost to follow-up for any other reason.

When a patient withdraws from Study Part One and does not continue on fingolimod, either in a study or non-study setting, they must return for two Follow-up visits, 3 months and 6 months after stopping study drug.

When a patient withdraws from Study Part Two, and does not continue on fingolimod, either in a study or non-study setting, they must return for one Follow-up visit, 3 months after stopping study drug.

If premature withdrawal occurs for any reason, the investigator must make every effort to determine the primary reason for a patient's premature withdrawal from the study and record this information on the appropriate eCRF.

Study drug must be discontinued for a given patient if the investigator determines that continuing it would result in a significant risk for that patient. In addition, study drug must be discontinued based on results of safety monitoring as outlined in [Appendix 5: Guidance on safety monitoring](#) and [Appendix 7: Guidance for Ophthalmic Monitoring](#). The following conditions/events may be considered sufficient to support a decision about the study drug discontinuation in individual cases:

- serious adverse event (e.g. cardiac failure, diagnosed malignancy, new neurological symptoms accompanied by MRI findings unexpected for MS) abnormal laboratory value(s) or abnormal test result(s) (e.g. ophthalmic findings).
- withdrawal of consent
- pregnancy (please see [Section 6.5.8](#) and [Section 7.3](#))
- use of prohibited medications, listed in [Section 4.2](#) and [Section 5.5.8](#).
- adverse events
- protocol deviation
- unsatisfactory therapeutic effect
- patient's condition no longer requires study treatment
- administrative problems (e.g. patient's non-compliance)
- discontinuation warranted as per local label requirements

In addition to scheduled visits, patients who discontinue study drug due to adverse events or abnormalities on safety monitoring tests must be followed up with additional visits as needed in order to confirm the resolution of abnormalities.

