## **7.2 Serious adverse event reporting**

To ensure patient safety, every SAE, regardless of suspected causality, occurring after the patient has provided informed consent and until 6 weeks after the patient has stopped study participation (defined as time of last dose of study drug taken or last visit whichever is later) must be reported to Novartis within 24 hours of learning of its occurrence.

Any SAEs experienced after this 6 week period should only be reported to Novartis if the investigator suspects a causal relationship to the study drug.

Recurrent episodes, complications, or progression of the initial SAE must be reported as follow-up to the original episode, regardless of when the event occurs. This report must be submitted within 24 hours of the investigator receiving the follow-up information. An SAE that is considered completely unrelated to a previously reported one should be reported separately as a new event.

Information about all SAEs is collected and recorded on the Serious Adverse Event Report Form. The investigator must assess the relationship of any SAE to study drug, complete the SAE Report Form in English, and send the completed, signed form by fax within 24 hours to the local Novartis Drug Safety and Epidemiology Department. The telephone and telecopy number of the contact persons in the local department of Clinical Safety and Epidemiology, specific to the site, are listed in the investigator folder provided to each site. The original copy of the SAE Report Form and the fax confirmation sheet must be kept with the case report form documentation at the study site.

Follow-up information is sent to the same person to whom the original SAE Report Form was sent, using a new SAE Report Form stating that this is a follow-up to the previously reported SAE and giving the date of the original report. The follow-up information should describe whether the event has resolved or continues, if and how it was treated, whether the blind was broken or not, and whether the patient continued or withdrew from study participation.

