9.1.2.1.2 Incidence rate of adverse events

The AE incidence rate (IR) is calculated per 100 patient-years. IR is defined as: the number of patients experiencing at least one event in a particular category, over the total patient-years of the “at risk” population for that event multiplied by 100. An underlying Poisson process for incidence rate within treatment group is assumed. For the summary time period for extension part 2, only AEs with a start date between first dose date of fingolimod during the study part 2 and the last dose date of fingolimod + 45 days will be counted; or SAEs with a start date on or after first dose date of fingolimod during the study part 2 will be counted.

To calculate the total patient-years (time at risk) of the “at risk” population:

1. For patients who have a particular AE category, sum the number of days from first dose date of fingolimod during the study part 2 to the first occurrence of that particular AE category
2. For patients who did not have a particular AE category, sum the number of days from first dose date of fingolimod during the study part 2 to last dose date of fingolimod + 45 days.
3. Add the time at risk for patients who had a particular AE category with the time at risk for patients who did NOT have a particular AE category. This is the total time at risk of that AE category.
4. Divide the total time at risk by 365.25.

Incidence rate of adverse events will be presented for the safety set. Incidence rate of AEs, AEs by relationship, excluding AE listed in the core data sheet, will be presented by PT. Similarly, all above indicated AE IR summaries will be conducted for SAEs.

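### SAE incidence rates count SAEs with no upper limit on onset date, while event-free patients contribute time only to last dose + 45 days, so events and time at risk cover different windows

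*SAP*

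**What the plan says.** **Part I SAP, 9.1.2.2.** Non-serious AEs count from first fingolimod dose to last dose + 45 days. For serious events: "All serious adverse events (SAEs) with onset on or after the first dose date of fingolimod among all studies are also included". The incidence rate divides patients with at least one event by total time at risk. Patients with the event contribute time to its first occurrence. For event-free patients the rule is to "sum the number of days from first dose date of fingolimod among all studies to last dose date of fingolimod + 45 days". The section then says: "Similarly, all above indicated AE IR summaries will be conducted for SAEs". It gives no separate time-at-risk rule for SAEs. The opening of section 9 exempts SAEs from the general + 45 day limit, so the open window is intended.

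**Part 2 SAP, 9.1.2.1.2.** The pattern is repeated inside the incidence-rate section: "SAEs with a start date on or after first dose date of fingolimod during the study part 2 will be counted", while event-free time runs "from first dose date of fingolimod during the study part 2 to last dose date of fingolimod + 45 days".

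**Protocol.** Section 7.2 requires every SAE to be reported until 6 weeks after the patient stops participation, "defined as time of last dose of study drug taken or last visit whichever is later". Suspected-related SAEs remain reportable after that. Patients who leave Part One and do not continue fingolimod are told that "they must return for two Follow-up visits, 3 months and 6 months after stopping study drug" (5.5.9). After Part Two such patients "must return for one follow-up study visit, 3-months post-last dose of fingolimod" (3.1). Patients who move to commercial drug are exempt from these visits.

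**The concern.** A rate per patient-year is interpretable only if the days on which an event would be counted are the days that enter the denominator. Here a patient followed off drug can add an SAE to the numerator well after day + 45, while a similar patient who stays event-free adds nothing for the same days. The all-AE rates share the problem only where a patient's first event in a category is an SAE after day + 45; for Part 2 the wording leaves this unclear.

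At stake are the SAE rates for the primary safety objective, which Part I plans by SOC, preferred term and risk term. A lesser flaw of the same kind is that the + 45 days is not stopped at death, so time can accrue to patients who have died.

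**Working it through.** The documents state no SAE rate, so there is no plan figure to reproduce.

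**1. Length of the unmatched period.** Protocol section 6 defines a month as 30 days; 6 weeks is 42 days. Let *w* be the number of days after last dose on which an SAE can still be counted in a followed patient.

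| | Capture ends at last follow-up visit | Capture ends 6 weeks later |
|---|---|---|
| Part One | *w* = 180; 180 − 45 = 135 unmatched days | *w* = 180 + 42 = 222; 222 − 45 = 177 |
| Part 2 | *w* = 90; 90 − 45 = 45 | *w* = 90 + 42 = 132; 132 − 45 = 87 |

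The larger figures are the upper reading of routine capture. Section 7.2 governs reporting to the sponsor's safety department, and no text says that SAEs after the last visit enter the analysis database.

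**2. Model.** Constant hazard *h* per day; *D* days from first to last dose; SAEs counted to *D* + *w*; event-free time to *D* + 45. Per patient:

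- P(event) = P = 1 − exp(−*h*(*D* + *w*))
- expected time = P/*h* − (*w* − 45)(1 − P)
- error = (ΣP / Σtime)/*h* − 1, weighted by the share followed, *f*

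The error is zero if *w* = 45 for everyone, positive for *w* > 45 and negative for *w* < 45.

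Assumptions, not in the documents: 1 SAE per 100 patient-years (*h* = 1/36525); *D* = 1826 (Part One, 5 years) or 730 (Part 2, 2 years); *f* as shown; *w* = 42 or 0 in patients without follow-up visits.

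**3. One case in full.** Part One, *D* = 1826, *f* = 50%, *w* = 222 in followed patients and 42 in the rest.

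- Followed: P = 1 − exp(−2048/36525) = 0.05453; time = 0.05453 × 36525 − 177 × 0.94547 ≈ 1824.3 days
- Rest: P = 1 − exp(−1868/36525) = 0.04986; time = 0.04986 × 36525 + 3 × 0.95014 ≈ 1823.9 days
- Per 1,000 patients: 52.19 events over 4,994.1 patient-years = 1.045 per 100, an error of +4.51%

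**4. Error with 42-day capture in the rest**

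| | 10% followed | 25% | 50% |
|---|---|---|---|
| Part One, *w* = 222 | +0.78% | +2.18% | +4.51% |
| Part One, *w* = 180 | +0.56% | +1.63% | +3.42% |
| Part 2, *w* = 132 | +0.76% | +2.48% | +5.35% |
| Part 2, *w* = 90 | +0.23% | +1.15% | +2.68% |

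For *w* = 222 and 50% followed, the error falls to +3.21% at 7 years (*D* = 2557) and +2.23% at 10 years (*D* = 3652). Protocol 3.3 speaks of 7 to 15 years of exposure.

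**5. Error with zero capture in the rest.** This would apply to Part Two entrants in the Part I analysis if Part I data stop at the end of Part I (Part I SAP section 1; Protocol 6.3 closes the dosing record there). It would also apply more widely if capture ends at the last visit.

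| | 10% followed | 25% | 50% |
|---|---|---|---|
| Part One, *w* = 222 | −1.19% | +0.53% | +3.41% |
| Part One, *w* = 180 | −1.41% | −0.01% | +2.33% |
| Part 2, *w* = 132 | −4.07% | −1.54% | +2.66% |
| Part 2, *w* = 90 | −4.60% | −2.88% | −0.01% |

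**6. Does rarity matter?** For *w* = 222 (42 in the rest), 5 years and 50% followed, the error is +4.64% at 0.1 SAE per 100 patient-years, +4.51% at 1 and +4.24% at 3. Relative bias barely depends on how rare the term is.

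**7. After matching.** With one end point on both sides, the model returns the true rate exactly.

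**The case against.** - **The wide SAE window is deliberate.** This stands. Section 9 of the Part I SAP exempts SAEs from the + 45 day limit, and keeping late serious events visible is defensible. It explains the numerator but does not supply a matching denominator.
- **The direction is not certain.** This stands in part. A reader might infer that the SAE rates are biased upward whatever the mix of patients. The documents do not support that: the 42-day capture in patients without follow-up visits is an assumption, and with zero capture the sign turns negative when few are followed. Time at risk also includes interruptions and gaps between studies, which pull the rate below a pure on-drug rate. That is a separate matter and does not cancel this one by design.
- **Rare terms.** A reader might infer that the bias is proportionally larger for preferred terms with few SAEs. It is not (step 6). One late SAE in a small category moves the estimate, but that is chance variation.
- **Consequences are limited.** This stands. Protocol 9.4.1 plans no inferential analyses. The yearly-interval tables stop at last dose, and the n (%) tables have no person-time denominator; neither is affected.

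**Conclusion.** The stated rule is wrong as written: in both SAPs the SAE rates draw events and time at risk from different windows, and no other text repairs this. In patients followed off drug the mismatch inflates the rate relative to one with matched windows.

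At 1 SAE per 100 patient-years, a constant hazard, 25 to 50% followed and 42-day capture in the rest, the error is about +1.6 to +4.5% in Part One at 5 years and +1.15 to +5.35% in Part 2 at 2 years. With little capture after last dose in the rest, the net sign is not established when few are followed (Part One, 5 years, 10% followed, *w* = 222, zero capture in the rest: −1.2%). The share followed and the extent of capture are not in the documents, so these figures are illustrative.

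The defect is the missing upper limit on SAE onset; it does not concern SAEs that lack a recorded end date. Severity is minor to moderate, because the study is descriptive and the pooled error is a few percent.

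**What to change.** In Part I SAP 9.1.2.2 and Part 2 SAP 9.1.2.1.2, define one end point for both events and time at risk in every incidence rate: the earliest of last dose + 45 days, death, and the end of SAE capture in that study part. Treat a patient whose first SAE in a category falls later as event-free for the rate. Keep later SAEs in the n (%) tables and in the follow-up-set summaries already planned in Part I SAP 9.1.2.1 and Part 2 SAP 9.1.2.1.1.

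Extending event-free time to the end of SAE collection is an equally valid matched rule and would keep late SAEs in the rate. Either choice should be stated.

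The cost is wording in two sections and one changed derivation, with an explicit definition of when SAE capture ends. No new data are needed. Under the first rule, late SAEs leave the rate but remain reported.

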## 6.2 Previous Study Details

In order to collect accurate information about the patient's previous fingolimod study details, the following records will be collected at the enrollment visit for each patient: the patient's previous fingolimod study number, center number, and patient number.

Upon the implementation of Amendment 4, the following information will be collected: the date of full approval for Amendment 4, whether or not the patient is re-enrolling into this study (defined as a patient who previously completed CFTY720D2399 based on the original study endpoint who is now re-entering the study using the originally assigned patient ID number) and the date of re-enrollment. In addition, data will be collected on any potential treatment gap during the time a patient may have temporarily been out of a fingolimod study and whether or not the patient went onto commercially available medication during the gap, if applicable.

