### **6.5.8 Pregnancy and assessments of fertility**

Pregnancy tests will be performed for all women as detailed in [Table 6-1](#) and [6-2](#). During Study Part One, visits requiring serum pregnancy tests will be performed by the central lab; those visits requiring urine pregnancy tests will be performed locally using a urine dipstick kit provided by the central lab. During Study Part Two, pregnancy tests will be performed locally, serum at visits where blood chemistry samples are collected, and urine at any other time points.

Patients becoming pregnant must interrupt the study drug. If patients interrupt treatment because of a pregnancy, they can remain in the study and re-start fingolimod treatment after delivery and discontinuation of nursing. Pregnant patients continuing in the study during dose interruption will need to have regular visits and complete assessments deemed safe for her by the Principal Investigator. Prior to resuming fingolimod therapy and the mandatory on-site first-dose monitoring, patients must have a negative serum pregnancy test and must no longer be nursing.

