6.1 Duration of exposure

The duration of exposure to fingolimod study drug will be defined as the number of days from first dose date of fingolimod among all studies to last dose date of the long-term follow-up study part I, excluding the days for which the patient did not take fingolimod (i.e., periods of temporary interruption). The number and percentage of patients being exposed for a minimum of ≥ 1 day, ≥ 90 days, ≥ 180 days, ≥ 360 days, etc. will be presented. Summary statistics of duration of exposure will also be provided. Patient-years of exposure will be reported and is calculated as the (sum of the total number of days on fingolimod study drug for all patients in the treatment group)/365.25. The above summaries will be presented for the fingolimod safety set and the subgroup of fingolimod safety set patients from Phase II/III studies.

Similar summaries will be provided for the duration of exposure to fingolimod study drug during the long-term follow-up study part I, which is defined as the number of days from first dose date of fingolimod in the long-term follow-up study to the last dose date, excluding the days for which the patient did not take fingolimod. Duration of exposure to fingolimod study drug during the long-term follow-up study part I will be presented for the safety set.

The fingolimod dose administration records during the long-term follow-up study part I will be listed for the safety set.

7 Concomitant medication

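### The adverse event incidence rates count time at risk when events are not being collected, and the serious-event numerator runs past its denominator, so the rates are distorted in both directions

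*SAP*

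**What the plan says.** Protocol 9.4.1.1 makes incidence per 100 patient-years a summary for the primary safety objective. Part I SAP 9.1.2.2 builds the denominator from two groups.

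- Patients with the event contribute time only until its initial onset: "For patients who have a particular AE category, sum the number of days from first dose date of fingolimod among all studies to the first".
- Patients without it: "sum the number of days from first dose date of fingolimod among all studies to last dose date of fingolimod + 45 days".

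The numerator takes "all non-serious adverse events with onset on or after first dose date of fingolimod among all studies to last dose date of fingolimod + 45 days". Serious events are taken from the first dose onward, and no end date is given.

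Part 2 SAP 9.1.2.1.2 keeps the same structure but starts the clock in Part 2: "from first dose date of fingolimod during the study part 2 to last dose date of fingolimod + 45 days". Its serious-event numerator is also open-ended.

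Other sections bear on whether events are collected during that time:

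- Protocol 3.1, for patients leaving at Part One: "Patients who choose to continue on commercial Gilenya outside the study are exempted from the follow-up visits". It makes the same exemption for the single Part Two follow-up visit.
- Part I SAP section 1 limits the analysis to data up to the end of Part I. Part 2 events are held in a Part 2 database (Part 2 SAP 9.1.2.1).
- Protocol 6.2, on re-enrolled patients: "data will be collected on any potential treatment gap during the time a patient may have temporarily been out of a fingolimod study", together with whether they used commercial drug meanwhile.
- Part I SAP 9.1.2 allows events from the gap before D2399 enrollment to be recorded. It does not mention the gap within D2399, between completing the study and re-entering it.
- Protocol 7.2 requires all SAEs to be reported until 6 weeks after the later of last dose and last visit. After that, only those suspected to be drug-related are reported.

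Part I SAP 6.1 computes exposure differently, "excluding the days for which the patient did not take fingolimod (i.e., periods of temporary interruption").

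**The concern.** A rate is interpretable when its events and its person-time come from the same observed period. Here they can diverge in two ways.

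First, person-time is credited when events are not being collected. This applies after death or loss to follow-up within the 45 days, after a move to commercial drug, after a move into Part Two (in the Part I analysis), and, in Part I, during off-study gaps before re-enrollment. It lowers the rate.

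Second, a serious event 100 days after the last dose enters the numerator, yet event-free patients followed just as long contribute only 45 of those days. This raises the rate.

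The SAP sees the first mechanism for relapses: section 8.1.2 warns that keeping the off-study time of re-enrolled patients can make the relapse rate look lower than it is. The adverse event rates carry no such warning, although safety is the primary objective and the study has no control arm in which the error could cancel.

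**Working it through.** The documents give no incidence rate, patient-years at risk, gap length, or number of patients who re-enrolled or moved to commercial drug. There is no figure to reproduce, and the sizes below are ranges under stated assumptions with a constant hazard.

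**Inputs from the documents.** Tail of 45 days = 45/365.25 = 0.1232 years. Exposure T of 7 to 15 years (protocol 3.3). T = 2 years for Part Two, about June 2016 to June 2018 (protocol 3.1). About 4,150 enrolled (Amendment 11 rationale). One month is 30 days (protocol section 6).

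**1. Uncollected 45-day tail, rare event.** Let f be the share of patients with no collection after the last dose. Planned rate / rate on observed time = T/(T + f × 0.1232).

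| T | f = 1 | f = 0.5 |
|---|---|---|
| 15 y | 15/15.1232: 0.8% low | 15/15.0616: 0.4% low |
| 7 y | 7/7.1232: 1.7% low | 7/7.0616: 0.9% low |
| 2 y | 2/2.1232: 5.8% low | 2/2.0616: 3.0% low |

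At f = 1 the tail adds at most 4,150 × 45/365.25 = 511 patient-years. For commoner events the effect is smaller, because patients with the event get no tail: at 10 per 100 patient-years it is 1.2% at 7 years and 5.3% at 2 years.

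For SAEs the tail matters little. Reporting covers at least 42 of the 45 days, so with no later visit the rate is low by 1 − (T + 42/365.25)/(T + 45/365.25): 0.1% at 7 years and 0.4% at 2 years.

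**2. Gaps (Part I only).** Let s be the share of patients with a gap, g its length in years, and k the hazard in the gap relative to on-study hazard times the fraction of gap events captured. Planned rate / on-study rate = (T + s·k·g)/(T + s·g). All three are assumed. At T = 7:

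- s = 10%, g = 90 days, k = 0: 7/7.0246, 0.4% low.
- s = 30%, g = 1 year, k = 0: 7/7.3, 4.1% low.
- Same s and g, k = 0.5: 7.15/7.3, 2.1% low.
- Same s and g, k = 1: 7.3/7.3, no bias.
- Same s and g, k = 1.5: 7.45/7.3, 2.1% high.

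Both sign and size depend on k, on which the documents are silent.

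**3. Open-ended serious-event numerator.** Suppose every patient is followed to F = T + d years, while event-free patients are credited C = T + 0.1232. With hazard λ, events per patient are D = 1 − exp(−λF) and person-years are D/λ − F·exp(−λF) + C·exp(−λF). The relative error is D/(λ × person-years) − 1. With λ = 0.01 per year:

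- d = 180 days (the second Part One follow-up visit): 5.0% high at T = 7, 2.3% high at T = 15.
- d = 180 days at T = 2: 17% high. Part Two has one follow-up visit, so full reporting runs to about 90 + 42 = 132 days. There, D = 0.02334, person-years = 2.1011, and the rate is 11% high.

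These are upper illustrations, because patients who continue on commercial drug are not followed that long.

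**The case against.** A reader might infer from the calendar-time denominator that every primary safety rate is too low, and that the rates contradict the SAP's own exposure table. The documents do not support either reading.

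- **On-study interruptions are observed.** A patient who interrupts for pregnancy is told that "they can remain in the study and re-start fingolimod treatment after delivery and discontinuation of nursing", with regular visits meanwhile (protocol 6.5.8). Non-serious events are counted over the same calendar window as the time, so both sides of the rate include the interruption. Removing it changes the question from any time since first dose to time on drug. That is a choice of estimand, not a bias correction.
- **The 45 days are plausible risk time.** Protocol 1.1 puts elimination at about 2 months.
- **Off-study is not the same as off-drug.** Re-enrolled patients had left because fingolimod was approved and reimbursed locally, so some may have been on commercial drug.
- **Much of the tail is observed.** Patients who stop fingolimod must return at 3 months, when adverse events are recorded. Part Two patients are by definition unable to obtain the drug elsewhere at entry, so f is probably well below 1 there, although the Part 2 SAP expects some to move to commercial drug.
- **Exposure and time at risk differ by design.** A first-event rate stops at the first event, so the totals would not agree even with identical gap handling.
- **The study is descriptive.** Counts, percentages and yearly-interval summaries ending at the last dose are also planned.

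All of these stand, and they rule out a general downward claim. They do not answer the remaining fault: nothing ends the clock when collection ends, nothing removes off-study gaps without collection, and the serious-event numerator and denominator cover different periods.

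**Conclusion.** The concern holds as a mismatch between events and person-time, not as a uniform understatement. Non-serious rates are too low to the extent that credited time was not under collection. Serious-event rates can be too high.

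The tail effect is bounded by the documents' own durations: at most about 1.7% at 7 years, 0.8% at 15 years and 5.8% at 2 years, assuming a constant hazard, a rare event and no patient observed after the last dose. With half observed, these are roughly halved. The serious-event error is about 2% to 5% at 15 to 7 years if all patients are followed to 180 days, and about 11% at 2 years if all are followed to 132 days, at an assumed 1 event per 100 patient-years.

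The gap effect cannot be sized from the documents. It is zero with full capture and equal hazard, and can take either sign otherwise. Overall the distortion is modest in Part I and larger in Part 2. It is worth correcting because these rates are themselves a main safety result.

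**What to change.** In Part I SAP 9.1.2.2 and Part 2 SAP 9.1.2.1.2:

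1. For event-free patients, end time at risk at the earliest of last dose + 45 days, death, and the last date on which that type of event was collected in the data analyzed. For SAEs, that last date is the end of the 6-week reporting period in protocol 7.2.
2. In Part I, exclude off-study gaps without adverse event collection from both numerator and denominator.
3. For the serious-event incidence rate, use one window on both sides. Keep later SAEs in the counts and listings.
4. Keep on-study interruptions in the main rate, and add a sensitivity rate on the on-drug exposure basis of SAP 6.1.
5. Add a caveat like the one in SAP 8.1.2 for relapses.

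The cost is SAP wording and some extra programming, with slightly fewer patient-years and a few events moved out of the rate. Study-drug interruptions are on the Dosage Administration Record, and gap data are collected under protocol 6.2. Exact dates of commercial use may not be available, but the main rate does not need them: off-study time without collection is excluded whether or not the patient was on drug.
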